15.4.2. Overdose

An overdose is any dose of study treatment administered to a subject or taken by a subject that exceeds the dose assigned to the subject according to the protocol. Overdoses are not considered AEs and should not be recorded as an AE on the eCRF; however, all overdoses must be recorded on an Overdose form and faxed to Biogen within 24 hours of the site becoming aware of the overdose. An overdose must be reported to Biogen even if the overdose does not result in an AE. If an overdose results in an AE, the AE must be recorded. If an overdose results in an SAE, both the SAE and Overdose forms must be completed and faxed to Biogen. All study treatment-related dosing information must be recorded on the dosing eCRF.

15.4.3. Medical Emergency

In a medical emergency requiring immediate attention, study site staff will apply appropriate medical intervention, according to current standards of care. The Investigator (or designee) should inform the study's Medical Monitor of the event as soon as it is feasible to do so. Refer to the Study Reference Manual's Official Study Contact List for complete contact information.

CONFIDENTIAL

The information contained herein may not be used, disclosed, or published without the written consent of
Biogen MA Inc.

15.4.3.1. Unblinding for Medical Emergency

In a medical emergency when knowledge of the subject's treatment assignment may influence the subject's clinical care, the Investigator or designee may access the subject's treatment assignment by IRT. When possible, the Investigator or designee should attempt to contact the study's Medical Monitor to discuss the emergency. The Investigator must document the reasons for unblinding in the subject's source documents. The Investigator is strongly advised not to divulge the subject's treatment assignment to any individual not directly involved in managing the medical emergency, nor to personnel involved with the analysis and conduct of the study. The Investigator can contact Biogen to discuss such situations.

15.5. Contraception Requirements

All women of childbearing potential and all men must practice highly effective contraception during the study and for 6 months after their last dose of study treatment. In addition, male subjects should not donate sperm for the duration of the study and for at least 6 months after their last dose of study treatment.

For the purposes of this study, women who do not meet one of the following criteria listed below are considered to be physiologically capable of becoming pregnant and are, therefore, defined as women of childbearing potential:

- Postmenopausal
 - 12 continuous months of natural (spontaneous) amenorrhea without an alternative medical cause and a serum follicle stimulating hormone level >40 mIU/mL
 - 6 weeks after surgical bilateral oophorectomy with or without hysterectomy
- Posthysterectomy
- Female surgical sterilization (e.g., bilateral tubal ligation)

For the purposes of the study, highly effective contraception is defined as use of 1 of the following:

For female subjects:

- Established use of oral, intravaginal, or transdermal combined (estrogen and progestogen containing) hormonal methods of contraception associated with the inhibition of ovulation.
- Established use of oral, injected, or implanted progestogen-only hormonal methods of contraception.
- Placement of an intrauterine device or intrauterine hormone-releasing system.

CONFIDENTIAL

The information contained herein may not be used, disclosed, or published without the written consent of Biogen MA Inc.

- Bilateral tubal occlusion.
- Sex with a male partner who has undergone surgical sterilization (with the appropriate postvasectomy documentation of the absence of sperm in the ejaculate).

For male subjects:

- A vasectomy with subsequent negative semen analysis.
- Sex with a woman who uses the methods described for female subjects if she is of childbearing potential.

True abstinence, when this is consistent with the preferred and usual lifestyle of the subject, can be considered an acceptable method of contraception based on the evaluation of the Investigator who should also take into consideration the duration of the clinical trial. Periodic abstinence (e.g., calendar, ovulation, symptothermal, postovulation methods) and withdrawal are not considered acceptable methods of contraception.

Pregnancy reporting is described in Section [15.4.1](#).

15.6. Safety Responsibilities

15.6.1. The Investigator

The Investigator's responsibilities include the following:

- Monitor and record all AEs, including SAEs, on the eCRF regardless of the severity, relationship to study treatment, relationship to the LP procedure, or relationship to the radioligand.
- Determine the seriousness, relationship to study treatment, relationship to the LP procedure, relationship to the radioligand, and severity of each event.
- Determine the onset and resolution dates of each event.
- Monitor and record all pregnancies in female subjects and follow up on the outcome of all pregnancies.
- Complete an SAE form for each SAE and fax it to Biogen within 24 hours of the study site staff becoming aware of the event.
- Pursue SAE follow-up information actively and persistently. Follow-up information must be reported to Biogen within 24 hours of the study site staff becoming aware of new information.
- Ensure all AE and SAE reports are supported by documentation in the subjects' medical records.

CONFIDENTIAL

The information contained herein may not be used, disclosed, or published without the written consent of
Biogen MA Inc.

- Pursue AE follow-up information, if possible, until the event has resolved or become stable. Record AE follow-up information, including resolution, on the eCRF, as applicable.
- Report SAEs to local ethics committees, as required by local law.

15.6.2. Biogen

Biogen's responsibilities include the following:

- Before study site activation and subject enrollment, the Clinical Monitor is responsible for reviewing with study site staff the definitions of AE and SAE, as well as the instructions for monitoring, recording, and reporting AEs and SAEs.
- Biogen is to notify all appropriate regulatory authorities, central ethics committees, central institutional review boards and Investigators of SAEs, as required by local law, within required time frames.

CONFIDENTIAL

The information contained herein may not be used, disclosed, or published without the written consent of
Biogen MA Inc.

16. STATISTICAL METHODS AND DETERMINATION OF SAMPLE SIZE

The objectives of the study and the endpoints to be analyzed are listed in Section 6.

16.1. Safety

16.1.1. Analysis Population

The safety population is defined as all subjects who received at least 1 dose of study treatment (BIIB054 or placebo). The same definition applies to Years 1 through 4.

16.1.2. Methods of Analysis

AEs will be coded using the Medical Dictionary for Regulatory Activities. In general, safety endpoints will be summarized using descriptive statistics.

Safety analyses will be done separately, as follows:

- Year 1 (placebo-controlled portion of the study): All data will be summarized by treatment group (e.g., placebo; 250 mg, 1250 mg, and 3500 mg of BIIB054; and total BIIB054).
- Years 2 through 4 (active-treatment dose-blinded portion of the study) and overall experience: Data from Years 2 through 4 and combined data from Years 1 through 4 (active-treatment dose-blinded portion of the study as well as overall experience on BIIB054 from the combined placebo-controlled portion and active-treatment dose-blinded portion of the study) will be summarized by treatment group.

The primary evaluation of safety will cover Year 1 of the study (placebo-controlled period, from baseline to Week 52).

Any safety data collected from in-clinic or remote visits will be included in the statistical analysis.

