5.5. Rationale for Dosing Regimen

In this study, subjects will receive an IV infusion of study treatment (placebo [Year 1 only] or BIIB054 250 mg, 1250 mg, or 3500 mg) once every 4 weeks. Subjects will receive a total of up to 41 doses: 13 doses in Year 1 (placebo-controlled portion of the study) and up to 28 doses in Years 2 through 4 (active-treatment dose-blinded portion of the study). The dose levels of BIIB054 were selected based on in vitro data on the affinity of BIIB054 to aggregated α -syn, nonclinical toxicology data, and BIIB054 safety, tolerability, and PK data from healthy volunteers in the Phase 1 human study.

In vitro studies established that BIIB054 binds to both soluble and aggregated forms of α -syn, with a higher apparent binding affinity for aggregates. The EC₅₀ of BIIB054 for aggregated α -syn was estimated at approximately 0.25 nM, and the EC₉₀ was estimated at approximately 2.1 nM (0.0375 and 0.315 μ g/mL, respectively). These EC₅₀ and EC₉₀ concentrations were used as target values for dose selection. See the BIIB054 Investigator's Brochure for further details.

In the Phase 1, first-in-human study (228HV101), serum and cerebrospinal fluid (CSF) concentrations in healthy volunteers were described using a population PK model. Subsequently, estimated PK parameters as well as between subject variability and residual variability estimates from healthy volunteers were used to simulate 1000 serum and CSF steady-state profiles. Emerging data from the PD cohort suggests that PK is similar between healthy volunteer and PD subjects. To account for weight differences between healthy

CONFIDENTIAL

The information contained herein may not be used, disclosed, or published without the written consent of Biogen MA Inc.

volunteers and the target Phase 2a population of PD subjects, the Parkinson’s Progression Markers Initiative study database was used as a source of weight distribution data in PD patients.

Simulations of CSF profiles in PD subjects were conducted for several dose levels to enable dose selection. CSF and brain interstitial fluid (ISF) concentrations of BIIB054 were assumed to be equal. Given the favorable safety profile of BIIB054 in the previous study 228HV101 and based on PK modeling from that study, a fixed-dose approach is to be implemented in this study.

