7.2.3. Follow-Up Visits and Final Visit

Follow-up visits are described in the following subsections.

Subjects who withdraw prematurely from the study will be asked to return to complete an Early Termination Visit within 4 weeks (± 3 days) of their last study treatment and a Final Visit 12 weeks (± 3 days) after their last study treatment.

7.2.3.1. Cohort A, Year 1

During Year 1, in addition to dosing day visits, subjects in Cohort A will return to the study site for 12 follow-up clinic visits on Days 2, 30, and 58 (24 hours after infusions 1-3); Days 4 and 60 (72 hours after infusions 1 and 3); Days 8, 36, and 64 (168 hours after infusions 1-3); Days 15 and 71 (336 hours after infusions 1 and 3); **1 visit only** at Week 22, 34, or 46; and at the Week 52 Visit.

A subject will return to the clinic for only 1 of the 3 visits at Week 22, 34, or 46 for PK sampling; the timing of the visit will be randomly assigned at the time of treatment assignment. However, should any subject have a scheduling conflict on the assigned date, the Investigator may reschedule to 1 of the other 2 timeslots.

During Year 1, subjects in Cohort A will have 1 Safety Telephone Call, on Day 43 (336 hours after the second infusion).

7.2.3.2. Cohort B, Year 1

During Year 1, in addition to dosing day visits, subjects in Cohort B will have 2 follow-up clinic visits: **1 visit only** at Week 22, 34, or 46; and the Week 52 Visit.

CONFIDENTIAL

The information contained herein may not be used, disclosed, or published without the written consent of Biogen MA Inc.

A subject will return to the clinic for only 1 of the 3 visits at Week 22, 34, or 46 for PK sampling; the timing for the visit will be randomly assigned at the time of treatment assignment. However, should any subject have a scheduling conflict on the assigned date, the Investigator may reschedule to 1 of the other 2 timeslots.

During Year 1, subjects in Cohort B will have 6 Safety Telephone Calls, on Days 2, 8, 30, 36, 58, and 64 (24 hours and 168 hours after each of the first 3 doses).

7.2.3.3. Cohorts A and B, Years 2 through 4

At the beginning of Year 2, in addition to the dosing visits, subjects will have 2 Safety Telephone Calls, 1 day and 7 days after Infusion 14 (the first infusion in Year 2).

[figure not shown]

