9.2. Randomization and Registration of Subjects

Subjects will be registered and randomized at Day 1, after all baseline assessments have been completed. In particular, prior to randomization at Day 1, the Investigator must verify that the subjects are eligible according to criteria in Section 8.1 and Section 8.2 (including confirmation of DaT deficit by central reader) and that the MDS-UPDRS results from Day 1 are available. No subject may begin treatment prior to assignment of a unique identification number (registration) and randomization. The identification number will be used on study-related documents pertaining to the subject. Any subject identification numbers that are assigned will not be reused even if the subject does not receive treatment.

CONFIDENTIAL

The information contained herein may not be used, disclosed, or published without the written consent of Biogen MA Inc.

Subjects will be randomized at Day 1 into 1 of 4 parallel dosing arms to receive placebo or BIIB054 (250 mg, 1250 mg, and 3500 mg). Cohort A (approximately 24 subjects) will be enrolled and randomized first in a 1:1:1:1 ratio. Randomization and dosing for Cohort B (approximately 287 subjects) will start after all subjects in Cohort A complete Week 12 assessments, and all available safety and PK data are reviewed by the IDMC. Randomization of subjects in Cohort B will be stratified by baseline (Day 1) MDS-UPDRS Part I + II + III total scores (≤ 35 and >35) and striatum SBR (≤ 1.2 and >1.2), and subjects will be randomized at Day 1 into 1 of 4 parallel dosing arms to receive placebo (n=82) or BIIB054 (250 mg [n=41], 1250 mg [n=82], or 3500 mg [n=82]) in each stratum.

All subjects who were randomized to receive placebo in Year 1 will be randomized, in equal ratio, to 1 of the active BIIB054 treatments for Year 2. For subjects receiving placebo in Cohort A, this randomization will occur prior to Infusion 14; for subjects receiving placebo in Cohort B, this randomization will occur at the time of the baseline Day 1 randomization (Year 1). Subjects who received BIIB054 (1250 mg or 3500 mg) in Year 1 will continue with the same dose regimen in Year 2. In addition, the decision of whether to randomize subjects who receive the 250-mg dose in Year 1 to 1 of the 2 highest doses of BIIB054 in Year 2 will be made after the IDMC review of Cohort A Week 12 data.

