16.1.2.1. Adverse Events

All analyses of AEs will be based on the principle of treatment emergence. An AE is considered to be treatment emergent if it has an onset date on or after the date of first dosing, or if it was present prior to the first dose and subsequently worsened. Incidences of all AEs will be presented by system organ class and preferred term by treatment group and overall active group. In addition, incidence of all AEs by severity, by relationship to study treatment, and by relationship to LP procedure will be presented. Data after subjects started symptomatic PD medications will be analyzed both ways (included and excluded).

CONFIDENTIAL

The information contained herein may not be used, disclosed, or published without the written consent of Biogen MA Inc.

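### The combined Year 1–4 AE table for BIIB054 reports incidence, although delayed starters have 52 weeks less time on drug; show it by start group and per patient-year

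*Protocol*

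**What the plan says.** Section 16.1.2 splits the safety analysis into Year 1 and a later part. The later part covers Years 2–4 and also a combined table in which "overall experience on BIIB054 from the combined placebo-controlled portion and active-treatment dose-blinded portion of the study) will be summarized by treatment group". Section 16.1.2.1 sets the AE measure: "Incidences of all AEs will be presented by system organ class and preferred term by treatment group and overall active group". It adds that AE data after the start of symptomatic PD medication will be analysed both included and excluded. Neither section mentions time on drug or says how a subject who switched from placebo is grouped in the combined table.

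Two statements in Section 16.1.2 limit the weight of these tables: "In general, safety endpoints will be summarized using descriptive statistics" and "The primary evaluation of safety will cover Year 1 of the study".

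Section 5.5 gives the dosing as "13 doses in Year 1 (placebo-controlled portion of the study) and up to 28 doses in Years 2 through 4". On the switch, Section 9.2 says: "All subjects who were randomized to receive placebo in Year 1 will be randomized, in equal ratio, to 1 of the active BIIB054 treatments".

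**The concern.** The combined table sets side by side subjects whose BIIB054 experience begins on Day 1 and subjects whose experience begins at Week 52. An incidence counts subjects with at least one event, so it rises with the length of observation. Two start groups with the same underlying rate will show different figures, and a reader could take the difference for an effect of early start or longer treatment. Evaluating dose-related safety is a secondary objective (Section 6), so these tables will be read closely even though they are descriptive.

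The analysis that excludes AEs after symptomatic PD medication has a related weakness. It shortens observation at an event after randomization that an effective disease-modifying drug could delay. Incidence without time at risk then depends partly on how long subjects stayed off that medication. Nothing in Section 16.1.2.1 confines this analysis to Years 2–4, so it also reaches Year 1.

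**Working it through.** **Schedule, from the protocol's own figures.** 13 + 28 = 41 doses (Section 5.5). 6 + 48 + 112 + 12 = 178 weeks (Section 7.2). Both stated totals reproduce. Dose k falls at Week 4(k − 1), so Infusion 14 is at Week 52, Infusion 25 at Week 96 and Infusion 41 at Week 160.

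**Gap between start groups.** With a last dose at Week 96, immediate starters receive 25 doses and delayed starters 25 − 13 = 12. With a last dose at Week 160 the counts are 41 and 41 − 13 = 28. The gap is 13 doses, or 52 weeks, in both cases.

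**Observation time.** Section 15.3.1 records AEs up to the Final Visit, which is 12 weeks after the last dose.
- Week 96 stop: 96 + 12 = 108 weeks for immediate starters and 108 − 52 = 56 for delayed starters.
- Week 160 stop: 160 + 12 = 172 and 172 − 52 = 120 weeks.

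**Incidence at equal true rates.** Incidence = 1 − exp(−rate × weeks/52). The rate is an assumption, because the documents give none. It is constant and the same in both groups, with no dropout.

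| Rate per year | Week 96 stop: immediate vs delayed | Week 160 stop: immediate vs delayed |
|---|---|---|
| 0.02 | 4.1% vs 2.1% | 6.4% vs 4.5% |
| 0.10 | 18.8% vs 10.2% | 28.2% vs 20.6% |
| 0.50 | 64.6% vs 41.6% | 80.9% vs 68.5% |

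At 0.10 per year the ratio is 1.84 with the Week 96 stop and 1.37 with the Week 160 stop.

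**Per patient-year.** Expected time to first event or end of observation is (1 − exp(−rate × time))/rate. At 0.10 per year and the Week 96 stop this is 0.188/0.10 = 1.88 years for immediate starters and 0.102/0.10 = 1.02 years for delayed starters. First events divided by that time give 10 per 100 patient-years in both groups, so the artefact disappears.

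**Years 2–4 window alone.** Both start groups enter at Week 52, follow Table 4 and stop by the same rule. With the Week 96 stop both have 56 weeks, hence 10.2% in both at 0.10 per year. The 52-week gap does not enter.

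**By dose, if switchers were pooled with their Year 2 dose.** Table 9 gives 101 placebo, 54 at 250 mg and 101 at each higher dose. Equal splitting gives 101/3 = 33.7 switchers per dose.
- Delayed share: 33.7/(54 + 33.7) = 38% at 250 mg and 33.7/(101 + 33.7) = 25% at 1250 and 3500 mg.
- Pooled incidence at 0.10 per year, Week 96 stop: (54 × 18.8 + 33.7 × 10.2)/87.7 = 15.5% at 250 mg, against (101 × 18.8 + 33.7 × 10.2)/134.7 = 16.6% at each higher dose.
- The difference is 1.1 points. Over assumed rates from 0.02 to 1.0 per year and both stop dates it runs from 0.3 to 3.1 points. The 1250 and 3500 mg groups are identical throughout.

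**PD-medication analysis.** This part is not sized. The documents give no rate at which subjects start the medication and no assumed effect of treatment on that rate.

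**The case against.** The strongest reply is that the protocol never prescribes a crude proportion. It speaks of incidences and descriptive summaries, does not exclude person-time rates, and an SAP that is not at hand may add them. That stands in part: the point is an improvement to a stated measure and does not show an error. It does not remove the point. Section 16.1.2.1 names the measure without deferring it, whereas the vital-sign and ECG sections (16.1.2.3 and 16.1.2.4) leave their definitions of abnormality to the SAP.

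Three stronger readings are tempting and not supported.

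- *All post-Year-1 incidences are distorted.* A reader might infer this from the shared paragraph in Section 16.1.2. The Years 2–4 window has the same entry, schedule and stop rule for both start groups, so the gap affects only the combined table.
- *The plan builds in a false dose effect.* This needs switchers to be pooled by dose, which the protocol does not state. Where it does define groups after Week 52, for efficacy in Section 16.5.2.2, it keeps delayed start separate. Even if pooled, the shift is small and does not separate 1250 from 3500 mg.
- *Delayed starters are monitored too thinly for AEs to be comparable.* The calls do differ. For Year 1: "During Year 1, subjects in Cohort B will have 6 Safety Telephone Calls". For Year 2: "subjects will have 2 Safety Telephone Calls, 1 day and 7 days after Infusion 14". Scheduled laboratory tests after first BIIB054 are also fewer for switchers: Weeks 60 and 96, against Weeks 12, 24, 36, 48 and 52 for Cohort B immediate starters. However, Table 6 adds panels 4 and 12 weeks after the last dose. Switchers have full examinations at Weeks 56 and 60, while Cohort B immediate starters have none between Day 1 and Week 52. The first ECG after starting drug comes at 4 weeks for switchers and at 12 for Cohort B immediate starters. AE recording is continuous and infusion visits are four-weekly throughout. No effect on AE capture can be shown from the documents.

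On consequence, the reply is right. Year 1 has the same planned length in all arms and is the primary safety evaluation, and the later tables carry no test. As for the PD-medication analysis, presenting it both ways helps, but it does not give the excluded version a time denominator.

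**Conclusion.** The point holds for the combined Year 1–4 BIIB054 tables. With equal true rates, incidence differs by start group solely because one group has 52 weeks less drug time: 18.8% versus 10.2% with a Week 96 stop and 28.2% versus 20.6% with a Week 160 stop. These figures assume a constant 0.10 per year, no dropout, follow-up to 12 weeks after the last dose, and a switcher's clock that starts at the first BIIB054 dose. The same choice of measure weakens the AE analysis that excludes data after PD medication, to an extent the documents do not allow one to size. It is a cheap improvement of modest importance.

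**What to change.** In Sections 16.1.2 and 16.1.2.1, or in the SAP with a cross-reference:

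- For the overall-BIIB054 AE tables, state how delayed-start subjects are grouped.
- Show those tables by immediate versus delayed start, and as subjects with a first event per 100 patient-years from first BIIB054 dose. Keep the crude counts alongside.
- In the AE analysis that excludes data after symptomatic PD medication, end each subject's time at risk at that start and report rates per patient-year.

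The cost is some wording and a few extra table columns. Dosing and event dates are already collected, so no new data are needed. The drawback is that a patient-year rate summarizes well only if the rate is roughly constant. If events cluster soon after first dosing, the group with shorter exposure will show the higher rate, which is a reason to keep the split by start group and the crude counts in view.
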